This study consists of two parts, the first phase involves the conduct of a cross-sectional study to assess the relationship between fructose consumption and the presence of NAFLD and the difference in several parameters, including anamnestic, clinical, auxological and hematochemical assays and the presence of the disease, and a second prospective part for the sociological evaluation one year after entering the study. It constitutes an extension of a study already approved by the University of Bari, approval of which is attached by the Independent Ethics Committee university hospital company "Consorziale Policlinico" with approval number CE/7331. The study involves the collaboration of three different units, respectively formed by the University of Eastern Piedmont (unit 1), University of Bari "A. Moro" (unit 2) and the University of Rome "Foro Italico" (unit 3). The first two units will enroll subjects with criteria of interest for the study. The University of Rome, on the other hand, will be concerned with the socioeconomic aspect of the study with the preparation of ad hoc questionnaires to be submitted to both children/adolescents and families.

Subjects

100 overweight or obese preschool children and adolescents visited at the Outpatient Clinic of Pediatric Endocrinology of the AOU Maggiore della Carità in Novara, at the Transition Endocrinology Outpatient Clinic of the SCDU Endocrinology and at the Outpatient Clinic of Pediatric Endocrinology "B.Trambusti" of the Giovanni XXIII Pediatric Hospital in Bari will be included in the study. Subjects will be selected continuously with adherence to the inclusion criteria from January 2024 until the end of December.

Inclusion criteria

- Children and adolescents with expression of informed consent according to art.2 quinque of Legislative Decree n.196/2003;
- Preschool children of both sexes aged 3 to 6 years and adolescents of both sexes aged 12 to 16 years;
- Children diagnosed with overweight (defined by BMI > 97th percentile for children younger than 5 years; and BMI > 85th percentile for children older than 5 years) or obesity (defined by BMI > 99th percentile for children younger than 5 years; and BMI > 97th percentile for children older than 5 years) (15,16).

Exclusion criteria

- Children and adolescents who are not in this age group;
- Children and adolescents with liver disease different than NAFLD;
- Children and adolescents with genetic type obesity or secondary obesity;

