Biochemical parameters according to clinical practice will be analyzed at the laboratories of Maggiore della Carità Hospital in Novara and at the laboratories of Giovanni XXIII Children's Hospital in Bari by estimation with Siemens Advia 2400 Healthcare Diagnostics, Siemens ADVIA chemistry XPT and in accordance with the respective protocols of reagent use.

Metaproteomic and metabolomics analysis will be conducted on stool, plasma and urine samples stored during the study for omics signature designation. Metaproteomic analysis with UPHLC-MS/MS mass spectrophotometer will be performed on stool samples to identify the presence of microorganisms in the gastrointestinal tract to be then correlated with the diet followed and clinical parameters of the patients. Peptides identified by the analysis will be entered into the UniProtKB, KEGG database and used for phylogenetic analysis.

Metabolomic analysis will be carried out on all three types of samples; metabolomics conducted on fecal samples will allow assessment of the functional activity of microorganisms, characterizing the intermediate phenotype that mediates host-microbiome interactions. Using one-dimensional gas chromatograph coupled with mass spectrometer (GC-MS-SPME), the metabolic profile and changes in metabolite levels in association with fructose intake will be identified. The identification of the main SCFAs will be carried out with the same instrument and then confirmed by injecting the appropriately treated samples into the instrument, comparing the retention time and the corresponding spectra obtained from GC-MS analysis. This method allows a metabolomic signature to be defined in relation to fructose consumption.

SAMPLE SIZE AND STATISTICAL METHODS

The study plans to enroll 100 children afferent to the centers previously listed. Given a first-type error of 0.05, a power of 80%, a variance of equal fructose consumption in the groups of children with and without NAFLD of 9.53 (pooled variance obtained from data reported in the article by Nier et al. (20), a ratio of 1:3 between children with and without NAFLD (expected prevalence in overweight and obese children ~24% (21)), the sample size will allow to highlight as statistically significant a minimal difference in the averages of fructose consumption between healthy and diseased children of 2.02 grams.

Statistical analysis

Evaluation of the relationship between fructose and NAFLD

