Descriptive statistics will be calculated in order to summarize the sociodemographic, perceptual, anthropometric, dietary, clinic-auxological, anamnestic and laboratory characteristics of the children included in the study.

Categorical variables will be summarized by absolute frequencies and percentages while numerical variables as mean and standard deviation (SD) or median and interquartile range (Q1-Q3) if not normally distributed according to the Shapiro Wilks test and quantile plot observation. The chi-square test or the corresponding nonparametric Fisher's test will be used to test the association between categorical variables and the presence of NAFLD while the t-test or the Mann-Whitney test will be used to test the difference in fructose consumption between children with NAFLD and those without the disease as well as the presence of differences between the two groups for the other numerical variables. The positive false discovery rate method will be used to account for the presence of multiple tests. Based on the number of NAFLD events observed, stratified analysis by age group (preschool age vs. adolescents) and center will be evaluated. **Regarding the assessment of bone metabolism, mean and standard deviation (SD) or median and interquartile range (Q1-Q3) of the parameters provided by the QUS overall and separately for high and low fructose consumption (below vs above median consumption) will be calculated.**

Microbiota analysis

Initially, an exploratory analysis of the relative abundance of the genera of bacteria in the microbiota will be carried out. The relative abundance of each species detected in the fecal samples will be represented by heatmaps. Next, a beta-diversity analysis will be performed comparing the complexity of genera

between subjects. Specifically, three matrices will be created based on weighted and unweighted Bray-Curtis and Unifrac distances that will be used to perform a principal coordinate analysis to highlight the presence of subject clusters based on the complexity of their microbiota.

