The “Linear discriminant analysis effect size” (LEFSE) method will be used to identify taxa that best discriminate between NAFLD-infected and non-infected patients. The LefSE method is an algorithm-based approach that performs the nonparametric Kruskal-Wallis and Wilcoxon rank-sum test to identify bacterial taxa whose relative abundance is statistically different between groups. Then discriminant analysis is applied considering only those bacterial taxa found to be significantly different between the two groups.

EXPECTED RESULTS

The present study is expected to gain new knowledge on the effect of fructose in relation to the onset of obesity-associated liver disease (NAFLD) and bone metabolism, with the identification of new biological, immunological, and omics markers that can be studied in the future as disease targets in the pediatric population. In addition, due to the scientific and sociological interest, the present study aims at the identification of sociodemographic and cultural determinants related to fructose intake, useful for the creation of preventive campaigns aimed at the promotion of a healthy lifestyle, with a change in eating habits that incentivize a healthy diet and a reduction of obesity status in the population. The results obtained, if statistically significant, will ultimately aim to develop effective preventive communication to promote a healthier lifestyle and diet in the population.

ETHICAL ASPECTS

The study was designed and will be conducted in accordance with international and national ethical standards on biomedical research with human beings, specifically:

- *Ethical principles for medical research involving human subjects* (Declaration of Helsinki -World Medical Association, current version);
- European Union *Standards of Good Clinical Practice* (ICH/GCP);
- *Convention on Human Rights and Biomedicine* (Oviedo Convention of 04/04/1997);
- Italian codes of ethics for health professions and specific current national regulations on clinical trials.

Management of informed consent

An information sheet explaining the type of study, purpose, procedures, sample and data collection, and possible benefits and risks of the research is available. This information will be presented to interested persons, who will have the freedom to give consent or to be able to withdraw it when the study has already begun.

Management of sensitive data

The following European and national regulations are kept in mind:

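### The LEfSe taxon screen (NAFLD vs no NAFLD) has no age-group or centre term, so if NAFLD prevalence differs clearly by age band or centre, taxa driven by that factor pass too often

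*Combined protocol and SAP*

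**What the plan says.** The *Microbiota analysis* section begins with heatmaps and a principal coordinate analysis of between-subject distances, which are descriptive. The only inferential step is LEfSe, which "will be used to identify taxa that best discriminate between NAFLD-infected and non-infected patients". It uses Kruskal-Wallis and Wilcoxon rank-sum tests to "identify bacterial taxa whose relative abundance is statistically different between groups", and the section continues: "Then discriminant analysis is applied considering only those bacterial taxa found to be significantly different between the two groups". No stratum, subclass or covariate is named at either step.

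The cohort is defined under *Subjects* and *Inclusion criteria* as "Preschool children of both sexes aged 3 to 6 years and adolescents of both sexes aged 12 to 16 years", enrolled in Novara and Bari.

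Age and centre do appear once, under the analysis of fructose and NAFLD: "Based on the number of NAFLD events observed, stratified analysis by age group (preschool age vs. adolescents) and center will be evaluated". The same paragraph adds: "The positive false discovery rate method will be used to account for the presence of multiple tests". Neither sentence is carried into the microbiota section.

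*Sample size and statistical methods* gives one overall prevalence of about 24% and a 1:3 ratio of children with and without NAFLD. No prevalence is given by age group or centre.

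**The concern.** The two age bands do not overlap, and the two units are in different cities. If a taxon's abundance differs by age or centre, and NAFLD prevalence differs by the same factor, the pooled comparison shows a NAFLD difference that is really an age or centre difference. The discriminant step then works on a list that already contains such taxa. False discovery rate control does not help, because it limits chance findings and a confounded association is not a chance finding.

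The analysis is secondary, and the primary fructose comparison is not affected. But *Expected results* looks for "omics markers that can be studied in the future as disease targets in the pediatric population". A taxon that marks adolescence or one clinic would be a poor candidate for that follow-up work.

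**Working it through.** **Basis for the group sizes.** The plan states no figure for LEfSe, so the group sizes come from its fructose calculation. With SD = √9.53 = 3.087 and 25 vs 75 children, the normal approximation to the detectable difference is (1.960 + 0.842) × 3.087 × √(1/25 + 1/75) = 2.00 g. The two-sided t calculation gives 2.017 g, which matches the stated 2.02 g. So 25 cases and 75 non-cases at two-sided 0.05 is a fair reading. The plan sets no separate alpha for LEfSe.

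**Assumed inputs.** There are 50 children per age band. Cases in preschoolers vs adolescents are 12 v 13 (24% vs 26%), 10 v 15 (20% vs 30%), 7 v 18 (14% vs 36%) or 5 v 20 (10% vs 40%). The taxon has no NAFLD effect but differs by age.

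**Hand calculation for a 1 SD age shift.** The spurious group difference is the shift times Δ, where Δ = (adolescent share of cases) − (adolescent share of non-cases). The pooled test sees an SD of √(1 + 1²/4) = 1.118, so its standard error is 1.118 × √(1/25 + 1/75) = 0.258. The true spread of the statistic is 1/1.118 = 0.894. With m = Δ/0.258, the pass rate is P(Z > (1.96 − m)/0.894) + P(Z < (−1.96 − m)/0.894).

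| Cases | Δ | m | Pass rate by hand | Simulated |
|---|---|---|---|---|
| 12 v 13 | 0.520 − 0.493 = 0.027 | 0.10 | 3.0% | 2.9% |
| 10 v 15 | 0.600 − 0.467 = 0.133 | 0.52 | 5.6% | 5.5% |
| 7 v 18 | 0.720 − 0.427 = 0.293 | 1.14 | 17.9% | 18.0% |
| 5 v 20 | 0.800 − 0.400 = 0.400 | 1.55 | 32.3% | 32.6% |

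**Simulated screening step** (40,000 replicates per cell; for two groups Kruskal-Wallis equals the two-sided rank-sum test):

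| Age-driven taxon, no NAFLD effect | 12 v 13 | 10 v 15 | 7 v 18 | 5 v 20 |
|---|---|---|---|---|
| Pooled, 0.5 SD shift | 4.4% | 5.0% | 8.5% | 12.4% |
| Pooled, 1.0 SD shift | 2.9% | 5.5% | 18.0% | 32.6% |
| Pooled, detected in 30% vs 60% | 4.1% | 5.4% | 10.0% | 16.1% |
| Pooled, detected in 5% vs 60% | 1.9% | 6.5% | 28.5% | 50.8% |
| Rank test stratified by age, or by age and centre | 4.7–5.1% in every cell | | | |

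Rates below 5% at near-equal prevalence arise because case counts were fixed and the pooled variance includes the age difference. A separate simulation with random case counts (overall prevalence 24%, 1.0 SD shift) gave 5.0% at 24%/24%, 8.1% at 19%/29%, 18.5% at 14%/34% and 35.3% at 9%/39%. The stratified test again gave about 5%.

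**Centre.** With assumed cases of 9 of 60 vs 16 of 40, the pooled pass rate is 9.2% (0.5 SD shift) and 21.1% (1.0 SD). Stratified by centre it is 4.9%.

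**After false discovery rate control.** The setting was 100 independent taxa, 10 related to NAFLD by 0.8 SD and 30 driven by age by 1 SD. Benjamini-Hochberg at 0.05 stood in for the positive false discovery rate. Mean false taxa over mean taxa listed:
- Pooled: 0.24/6.48 = 4%, 0.34/6.60 = 5%, 0.96/7.40 = 13%, 2.63/9.27 = 28%.
- Age-stratified: 0.31/6.47, 0.33/6.42, 0.30/5.96 and 0.26/5.34, each about 5%.

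The discriminant step was not simulated, because the plan gives no cut-off for it.

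**The case against.** The strongest objection concerns the reading of LEfSe. With two groups, Kruskal-Wallis and the rank-sum test coincide, so naming both may imply a second step run within subgroups. If that step required significance in the same direction within each age band, an age-driven taxon would pass at most 0.24% of the time. This makes the plan's wording ambiguous, but it does not close the gap. No subclass is named, the section describes the tests as between the NAFLD groups, and that strict rule would have only 26–41% power for a 0.8 SD effect.

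Second, the plan already recognises age and centre. That is true, and the gap is only that the stratification is conditional and not extended to the taxon screen.

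Third, no bias is shown from the documents. This stands: apart from the 1:3 ratio, every input is assumed, and with fixed case counts a 10-point prevalence difference gives only 5.0–6.5%. Material inflation needs a gap of roughly 20 points or more, or a taxon strongly tied to age.

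Fourth, naming subclasses in LEfSe would be a smaller change than adding a stratified test. It would resolve the ambiguity, but at the power just quoted under the strict rule, and with about 25 cases over four strata one combined test is more workable than separate within-stratum tests.

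**Conclusion.** The concern holds in its conditional form. The only microbiota test in the plan compares NAFLD groups without an age or centre term, in a cohort where either factor could confound it. At equal or nearly equal prevalence there is no inflation. At 14% vs 36% an age-driven taxon passes about 9–29% of the time, and at 10% vs 40% about 12–51%, depending on how strongly it tracks age. These figures rest on assumed prevalence splits and taxon differences, and they cover the screening step only. Since the analysis is secondary and hypothesis-generating, this is an improvement the plan should make, not a threat to the primary result.

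**What to change.** 1. Base NAFLD–taxon conclusions on a per-taxon rank test stratified by age group and centre (van Elteren, four strata), fixed in advance and not conditional on event count. It held 4.6–5.1% even with preschool strata of 1 and 1 or 0 and 3 cases; a stratum without cases contributes nothing. Stratifying by age alone can leave centre bias: 6.9% vs 5.0% with four strata, for cases 2/5/6/12 by cell and shifts of 1.0 SD by age and 0.5 SD by centre. A covariate-adjusted model suited to zero-inflated abundances is an alternative.
2. State that the positive false discovery rate rule applies across all taxa tested.
3. Keep LEfSe as an unadjusted descriptive display.

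The change needs SAP wording and computation on data already collected. The price is power for a 0.8 SD effect:

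| Setting | Four strata (12 v 13 / 7 v 18 / 5 v 20) | Pooled |
|---|---|---|
| Unadjusted 0.05 | 91 / 89 / 87% | 92% (no age shift) |
| FDR over 100 taxa, 10 related | 60 / 54 / 50% | 62–63% |
| FDR over 100 taxa, 1 related | 38 / 32 / 29% | 39% |

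At unadjusted 0.05, power falls to 82–84% with the sparsest strata. After FDR, four-strata stratification costs about 1 point (39 − 38) to 13 points (63 − 50); the rest of the drop comes from FDR itself. Fewer taxa will be declared.

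### The LEfSe screen states no multiplicity adjustment across taxa, and the plan's false-discovery-rate sentence is not clearly extended to it

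*Combined protocol and SAP*

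**What the plan says.** All references are to the combined protocol and SAP.

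- **Microbiota analysis.** LEfSe is used "to identify taxa that best discriminate between NAFLD-infected and non-infected patients". It is described as per-taxon Kruskal-Wallis and Wilcoxon rank-sum testing, followed by a second step: "Then discriminant analysis is applied considering only those bacterial taxa found to be significantly different between the two groups". The section gives no significance level, adjusted p-value, discriminant score cut-off, subclass, number of taxa, hold-out sample or resampling.
- **Evaluation of the relationship between fructose and NAFLD.** After the chi-square/Fisher and t/Mann-Whitney comparisons comes the plan's only multiplicity statement: "The positive false discovery rate method will be used to account for the presence of multiple tests". It gives no level and no list of the tests covered. The Microbiota analysis heading comes afterwards.
- **Sample size and statistical methods.** The one stated error rate belongs to the fructose comparison: "Given a first-type error of 0.05, a power of 80"%. The group sizes follow from "The study plans to enroll 100 children afferent to the centers previously listed" and "a ratio of 1:3 between children with and without NAFLD".
- **Expected results.** Omics markers are promised as candidates for later study.

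**The concern.** An analyst who follows the microbiota section as written has a complete rule: test each taxon, keep those that differ significantly, and pass them to the discriminant analysis. Nothing in that rule adjusts for the number of taxa. The expected number of false taxa then grows in proportion to the number tested, and with many taxa the list would almost never be empty, whether or not NAFLD is related to the microbiota. This would happen even with groups perfectly balanced on age and centre.

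Naming two tests may look like a double safeguard, but with two groups and no subclass it is one test done twice.

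The discriminant step also appears to use the same children as the screen, since no split is described. A taxon that passed partly by chance therefore enters with an exaggerated difference.

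At stake is the list of candidate taxa, one route to the omics markers the study hopes to carry forward.

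**Working it through.** **1. The plan's own figure, to fix the group sizes.** Inputs: N = 100 and ratio 1:3, giving 25 and 75; variance 9.53 ("a variance of equal fructose consumption in the groups of children with and without NAFLD of 9.53"); alpha 0.05, taken as two-sided; power 80%.

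- SD = √9.53 = 3.087
- Standard error = 3.087 × √(1/25 + 1/75) = 3.087 × 0.2309 = 0.713
- Normal approximation: (1.960 + 0.842) × 0.713 = 1.997 g
- Noncentral t: 2.017 g

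This reproduces "a minimal difference in the averages of fructose consumption between healthy and diseased children of 2.02 grams". So 25 against 75 is the intended split, and I use it below. The plan gives no corresponding figure for LEfSe.

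**2. Do the two tests protect twice?** For two groups, the Kruskal-Wallis statistic equals the square of the Wilcoxon rank-sum z statistic (no continuity correction) and is referred to chi-square on 1 degree of freedom, so the p-values are identical. On one simulated data set of 25 against 75, both gave p = 0.1052. The second test adds nothing unless a subclass is specified, and none is.

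**3. False taxa under no true relation.** Assumptions: M taxa tested, each at an unadjusted 0.05. The documents give neither for LEfSe.

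- Expected false taxa = 0.05 × M
- Chance of at least one, if independent = 1 − 0.95^M

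I also simulated log-normal compositional abundances for 25 against 75 children, 1,000 runs per setting, with uncorrelated and with correlated taxa. The last column applies Benjamini-Hochberg at 5% to the same p-values.

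| Taxa M | 0.05 × M | 1 − 0.95^M | At least one, simulated | At least one, with BH 5% |
|---|---|---|---|---|
| 20 | 1.0 | 64.2% | 59.1-59.9% | 4.4-4.6% |
| 50 | 2.5 | 92.3% | 86.6-89.1% | 3.9-4.8% |
| 100 | 5.0 | 99.4% | 97.9-99.0% | 4.2-4.5% |
| 200 | 10.0 | >99.9% | 99.9-100% | 3.1-4.1% |

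A smaller simulation of the same kind (400 runs per setting, 50 to 200 taxa) gave 2-4% with Benjamini-Hochberg.

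An approximate LDA-type score cut-off of 2 does not rescue the unadjusted screen. The chance of at least one false taxon was still 57-59% at M = 20 and 96-97% at M = 100.

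**4. Selecting and fitting on the same children.** I took 100 taxa, of which 3 truly differ by 0.5 SD, and a 5% Benjamini-Hochberg gate. The truly different taxa that passed showed a mean difference of 0.90 SD, so effect sizes are inflated even after adjustment. A discriminant rule fitted to the passing taxa had a mean AUC of 0.77 in the same children against 0.62 in new ones. The plan promises no AUC; this only illustrates the optimism.

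**The case against.** The strongest reply is that the plan already controls multiplicity. The false-discovery-rate sentence is worded generally. It follows a sentence that extends two-group testing to the other numerical variables, and a taxon's relative abundance compared between the same two groups is that kind of variable. Nor does the heading strictly bound its content, since the bone ultrasound summaries by fructose level sit under it too. This stands in part. A reader might infer that the plan has ruled out adjustment for taxa, and the documents do not support that. They leave the scope open, and if the method does cover the screen, most of the false-taxon problem goes away.

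Three other strong readings also go too far:

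- **That false taxa are certain.** This needs a level and a taxon count. The 0.05 belongs to the fructose calculation, and with 20 taxa the chance is about 60%.
- **That the plan will report an inflated classifier.** No AUC, prediction rule or classification performance is planned. LEfSe is used here to find and rank taxa, so cross-validation is needed only if performance is reported.
- **That LEfSe is the only inferential use of the microbiota data.** The mass spectrometry section also plans to correlate the organisms found with diet and clinical parameters, and omics markers may come from metabolomics.

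A subclass such as age group or centre would make the second test non-redundant. The plan says stratification by these will be considered, but not within LEfSe.

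Finally, the omics work is a secondary aim and its markers are for future study. That lowers the consequence. However, the plan applies the word exploratory to the initial abundance description, not to LEfSe.

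**Conclusion.** The concern holds as a gap in scope with a measurable consequence. The LEfSe paragraph states its own entry rule without adjustment, and the false-discovery-rate sentence is not clearly extended to it. Followed literally, with an unadjusted 0.05 and no true relation, the screen yields on average 1 false taxon with 20 tested, 2.5 with 50, 5 with 100 and 10 with 200. The chance of at least one is about 60%, 90%, 99% and over 99%. Adjustment at 5% brings this to about 2-5%.

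These figures rest on the assumed level, the assumed taxon counts, a 25 to 75 split with usable stool data from all 100 children, and simulated abundance distributions. Benjamini-Hochberg stands in for the positive false-discovery-rate method, whose level the plan does not give. That screening and discriminant fit use the same children is inferred from the absence of any described split.

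This should be corrected, but it does not bear on the fructose comparison for which the study is sized.

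**What to change.** In the Microbiota analysis section, state that:

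1. the plan's false-discovery-rate method, at a named level, is applied across all taxa tested at the LEfSe screening step;
2. only taxa that pass it enter the discriminant analysis;
3. if none passes, the result is reported as no discriminating taxon found;
4. effect sizes for the selected taxa are hypothesis-generating, because selection and fit use the same children.

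If, and only if, classification performance is reported, take it from cross-validation with the taxon selection repeated inside each fold.

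The cost is a few sentences and negligible computing. The real downside is that fewer taxa will be declared, including some that truly differ.
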